5.2.2. Alternate predictors of response

5.2.2.1 Tier A biomarker panel

The Tier A biomarkers panel consists of inflammation-related analytes: IL-6, IL6R, IL-10, IL-1b, and TNFa. Kynurenine pathway metabolites kynurenine, tryptophan, 3-OH kynurenine, kynurenic acid, and quinolinic acid are also included in Tier A as this pathway has been shown to drive inflammatory processes.

 Δ_{w12}^{HDRS17} will be modeled as a function of each analyte in the high-priority panel measured at baseline with BMI, sex, and age as covariates. Analyte levels that model a significant amount of variance (p ≤ 0.1) in Δ_{w12}^{HDRS17} will be compared against performance of the baseline hsCRP model from Section 5.2.1 Model performance will be compared using Akaike Information Criterion (AIC) or non-parametric equivalent. Bonferroni Family Wise Error Rates (FWER) will be reported in addition to uncorrected p values. Models with FWER ≤ 0.1 and better performance than the hsCRP model are identified as alternate candidate predictive biomarkers.

Logistic models for identified alternate candidate biomarkers, if any, will be generated for predicting remission and response and the results will be compared to the corresponding outcome of logistic models for baseline hsCRP in Section 5.2.1.

Multivariate models using supervised machine learning will also be used to predict Δ_{w12}^{HDRS17} , response, and remission using hsCRP and Tier A analytes. 80% of the samples will be used for training with 20% set aside for model testing. ROC curves will be generated for each of model in addition to AUC and model accuracies.

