1.4. Sample Size Justification

Approximately 192 subjects will be enrolled in this study, with approximately 96 subjects randomized per treatment group.

The target study population is male and female subjects with MDD who have had a suboptimal response to standard oral antidepressant therapy; have failed no more than 3 antidepressant treatments in the current major depressive episode; approximately 142 subjects with screening hsCRP $\geq 0.300 \text{ mg/dL}$ (SI 3.00 mg/L) and approximately 50 subjects with screening hsCRP<0.300 mg/dL (SI 3.00 mg/L) will be enrolled.

The expected final sample size of 142 for subjects with screening hsCRP ≥ 0.300 mg/dL (SI 3.00 mg/L) was determined based on the assumption of an effect size of at least 0.5 for the HDRS17 (mean change from baseline to week 12 endpoint between the sirukumab and placebo groups of 4 with SD=8). This is considered to be a clinically relevant difference in a population with suboptimal response to standard oral antidepressant therapy. Power is set at 90.0%, with a 1-sided alpha of 0.125 and a 12-week drop-out rate of 25%. It was also assumed that 10% of the randomized subjects would be excluded from the primary efficacy analysis due to having hsCRP ≥ 3.00 mg/L at screening but not at baseline.

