2.5.3. Biomarker Analysis Set

Biomarker analyses will be performed on biomarker analysis set. It will include all randomized subjects who receive at least 1 dose of study drug in the double-blind phase and have at least 1 sample obtained.

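### The machine-learning models appear to be judged on a single 20% hold-out of about 14 (sirukumab) or 29 (pooled) subjects, too few to separate moderate discrimination from none or to compare models

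*SAP*

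**What the plan says.** SAP section 5.2.2.1 (Tier A panel) plans supervised machine-learning models for the Week 12 HDRS17 change, response and remission. On evaluation it says "80% of the samples will be used for training with 20% set aside for model testing", followed by ROC curves, AUC and accuracy for each model. Section 5.2.2.2 (full panel) repeats the sentence. There the models are built once on the analytes that pass a univariate screen at uncorrected p ≤ 0.1 and once on all analytes.

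Neither section mentions cross-validation, repeated splitting, stratification of the split by outcome, or an interval for the AUC.

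The population is not fixed either. The biomarker analysis set (2.5.3) is "all randomized subjects who receive at least 1 dose of study drug in the double-blind phase and have at least 1 sample obtained", which covers both arms. The reference hsCRP models in 5.2.1 are fitted to the sirukumab arm, with placebo modelled separately. The machine-learning paragraphs do not say which they follow.

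The sizes come from section 1.4: "Approximately 192 subjects will be enrolled in this study, with approximately 96 subjects randomized per treatment group", with a "12-week drop-out rate of 25" per cent.

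**The concern.** All the predicted outcomes are Week 12 outcomes, so the usable sample is roughly the Week 12 completers, and one fifth of them is a very small test set. An AUC or accuracy from it depends heavily on which subjects happen to fall into it, and the remaining four fifths add nothing to the estimate of performance.

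These models are the SAP's multivariate look at whether markers predict response and remission, which belongs to exploratory objective 2 in section 1.1. Section 5.2.2.2 also invites a comparison between the screened and the all-analyte model. A point AUC without an interval, from so few subjects, could make a useless panel look promising or hide a useful one.

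**Working it through.** **1. The plan's own figure.** Section 1.4 gives a difference "between the sirukumab and placebo groups of 4 with SD=8" and "Power is set at 90.0%, with a 1-sided alpha of 0.125 and a 12-week drop-out rate of 25" per cent, and adds "It was also assumed that 10% of the randomized subjects would be excluded from the primary efficacy analysis". Per arm, n = 2 × (1.1503 + 1.2816)² × (8/4)² = 47.3. Inflating, 47.3 / 0.75 / 0.90 = 70.1, so 71 per arm and 142 in total. This matches "The expected final sample size of 142 for subjects with screening hsCRP" and confirms how the 25% drop-out is used. The 10% exclusion concerns only the primary analysis and is not applied below.

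**2. Test-set size.** Applying the 25% to all 192 subjects is an assumption, because section 1.4 uses it for the 142.
- Sirukumab only: 96 × 0.75 × 0.20 = 14.4
- Both arms: 192 × 0.75 × 0.20 = 28.8
- With no drop-out: 96 × 0.20 = 19.2 and 192 × 0.20 = 38.4

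**3. Precision of the AUC.** Hanley-McNeil, with A the true AUC, m events and n non-events:

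SE² = [A(1−A) + (m−1)(Q₁−A²) + (n−1)(Q₂−A²)] / (mn), where Q₁ = A/(2−A) and Q₂ = 2A²/(1+A).

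At A = 0.70, Q₁−A² = 0.0485 and Q₂−A² = 0.0865. For 14 subjects with 4 events: SE² = (0.21 + 3 × 0.0485 + 9 × 0.0865)/40 = 0.0283, so SE = 0.168 and the 95% half-width is 1.96 × 0.168 = 0.33.

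The SAP states no event rates, so a range is assumed. Events are rounded to whole subjects.

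| Event rate | 14 subjects, half-width at AUC 0.70 | 29 subjects, half-width at AUC 0.70 | 14 subjects, lower limit at AUC 0.80 | 29 subjects, lower limit at AUC 0.80 |
|---|---|---|---|---|
| 15% | 0.44 | 0.31 | 0.41 | 0.53 |
| 20% | 0.37 | 0.26 | 0.47 | 0.57 |
| 30% | 0.33 | 0.22 | 0.51 | 0.61 |
| 40% | 0.29 | 0.20 | 0.55 | 0.63 |
| 50% | 0.28 | 0.19 | 0.56 | 0.63 |

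At AUC 0.70 the 14-subject interval includes 0.5 at every rate. The 29-subject lower limit runs from 0.39 (15%) to 0.51 (50%), so at best it only just clears 0.5. With no drop-out the half-widths at AUC 0.70 are 0.24 to 0.36 (19 subjects) and 0.17 to 0.25 (38 subjects).

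**4. Check by simulation.** Wald limits are crude with few events and can exceed 1. In 20,000 binormal draws at true AUC 0.70, the central 95% of observed AUCs was 0.38 to 0.98 with 14 subjects (4 events) and 0.48 to 0.89 with 29 (9 events). The observed AUC was 0.5 or below in 13% and 4% of draws.

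**5. Sparse remission.** At an assumed 15% rate, 14 test subjects contain no remitter with probability 0.85¹⁴ = 0.10, which leaves the AUC undefined. They contain at most two with probability 0.65.

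**6. Comparing two models on the same test set.** SE of the difference = SE × √(2(1−r)), with r the correlation between the two AUCs (assumed). At AUC 0.70 and 30% events, the half-width of the difference is 0.33 (14 subjects) and 0.22 (29) for r = 0.5, and 0.21 and 0.14 for r = 0.8. A difference of 0.10 is not resolved in any of these cases.

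**7. Accuracy.** At a true accuracy of 0.70, 1.96 × √(0.7 × 0.3/N) = 0.24 for 14 subjects and 0.17 for 29.

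**8. If every completer is predicted out of fold.** At AUC 0.70 and an assumed 35% response rate, unrounded counts give a half-width that falls from 0.30 (14.4 subjects) to 0.13 (72), and from 0.21 (28.8) to 0.09 (144). These full-sample figures ignore the correlation between folds and are therefore optimistic.

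**The case against.** A reader might infer that the hold-out AUC can support no conclusion at all. The figures do not bear that out. At AUC 0.80 the pooled interval excludes 0.5 at every rate from 15% to 50%, and the 14-subject interval does so from about 30% upward. The shortfall concerns moderate discrimination and comparisons between models.

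A reader might also take it as stated that only one split is made. The SAP does not say so. It sets 20% aside, and a single hold-out is the natural reading, but repeated splits and cross-validated tuning within the training part are not excluded. Tuning of that kind would not enlarge the test set, and if repeated splitting is intended the SAP needs to say so.

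Thirdly, a reader might infer that biomarker selection hangs on this AUC. It does not. Section 5.2.2.1 names alternate candidates by a Bonferroni-adjusted level of 0.1 and better performance than the hsCRP model, and that rule applies to the univariate regressions, for which no split is stated. No AUC threshold is set anywhere. This objection stands and limits the consequence.

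Two further limits also stand. The event rates are assumptions. And the models predict the continuous HDRS17 change as well, for which no precision figure is worked out here.

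**Conclusion.** The point holds as a weakness of an exploratory analysis. On the natural reading, performance is estimated in about 14 or 29 subjects, and at a true AUC of 0.70 the 95% half-width is about 0.28 to 0.44 or 0.19 to 0.31. That is too wide to separate moderate discrimination from none reliably, or to compare models.

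The result rests on three things: the 25% drop-out applied to all 192 subjects, event rates assumed between 15% and 50%, and a single split inferred from the text. Removing the drop-out narrows the intervals but does not change the conclusion for the sirukumab-only set. In the pooled set of 38, the lower limit at AUC 0.70 reaches or slightly exceeds 0.5 from about 30% events upward. The primary and secondary efficacy analyses and the formal candidate-biomarker rule are untouched.

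**What to change.** In sections 5.2.2.1 and 5.2.2.2:
- Replace the single split with repeated k-fold cross-validation stratified by outcome, for example 5 folds and 50 repeats.
- Redo every data-dependent step inside each training fold: all tuning and, in 5.2.2.2, the univariate screen at p ≤ 0.1. The SAP does not now confine that screen to training data. Screening on the full sample would bias the AUC upward, and cross-validating afterwards would only make the biased figure look precise.
- Report out-of-fold AUC and accuracy for response and remission, and out-of-fold R² for the HDRS17 change. Give intervals that allow for correlated folds, for example a bootstrap of the whole procedure that keeps copies of the same subject in one fold.
- State whether the models use the sirukumab arm only or both arms.

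The cost is SAP wording and more computing; no new data are needed. The downside is that no untouched hold-out remains, but one of 14 to 29 subjects has limited value.

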5.2.2.2 Full biomarker panel

If analysis of high-priority analytes fails to identify alternate candidate predictive biomarkers, exploratory univariate modeling of Δ_{w12}^{HDRS17} will be carried out with each of the remaining baseline biomarkers. Modeling outcomes will be tabulated including uncorrected p-values as well as p-values adjusted by controlling the Benjamini & Hochberg False Discovery Rate (BH FDR). Scatter plots for regression models with uncorrected p-values ≤ 0.05 will be created and annotated with coefficients of determination (R² and R²_{partial}) and R²_{reduced} for the reduced model.

Multivariate models using supervised machine learning will also be used to predict Δ_{w12}^{HDRS17} , response, and remission using all analytes that reach significance predicting Δ_{w12}^{HDRS17} at uncorrected p ≤ 0.1 in the univariate models. 80% of the samples will be used for training with 20% set aside for model testing. ROC curves will be generated for each of model in addition to AUC and model accuracies. Results from multivariate modeling will also be reported using all analytes regardless of univariate significance.

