5. BIOMARKERS

5.1. Biomarker Variables

Biomarkers consist of hsCRP, ACTH, Adiponectin, serum BDNF, IGF1, IL6R, Leptin, IL-6, IL-1b, IL-10, TNFa, saliva Cortisol, serum Cortisol, Kynurenine pathway metabolites, and a total of 92 SNPs related to above HPA, metabolic, and inflammatory biomarkers.

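### Section 5.2.2.2 picks the machine-learning inputs at p ≤ 0.1 before the 80/20 split, so the test AUC of those models is biased upward

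*SAP*

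**What the plan says.** SAP section 5.2.2.2 applies when the Tier A analysis (5.2.2.1) has found no alternate candidate biomarker. It has three steps, in this order:

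1. Univariate modelling of the Week 12 HDRS17 change "will be carried out with each of the remaining baseline biomarkers". The output is a table: "Modeling outcomes will be tabulated including uncorrected p-values as well as p-values adjusted by controlling" the Benjamini-Hochberg false discovery rate.
2. Machine-learning models of change, response and "remission using all analytes that reach significance predicting" the HDRS17 change "at uncorrected p ≤ 0.1 in the univariate models".
3. The split, named in the next sentence: "in the univariate models. 80% of the samples will be used for training with 20% set aside for model testing". A ROC curve, AUC and accuracy follow for each model.

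A second, unfiltered set is also planned: "Results from multivariate modeling will also be reported using all analytes regardless of univariate significance". Section 5.1 counts among the biomarkers "a total of 92 SNPs related to above HPA, metabolic, and inflammatory biomarkers". The biomarker analysis set (2.5.3) defines no hold-out sample, and no cross-validation or nested selection is described.

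**The concern.** A hold-out sample gives an honest performance estimate only if it plays no part in building the model, and choosing the inputs is part of building it. The filter points back to the tabulated univariate models, which carry no training restriction. The filter outcome is the Week 12 HDRS17 change, and response and remission derive from the same Week 12 score. A marker that happens to correlate with outcome in the test subjects is therefore more likely to be selected, and the same chance correlation then counts as predictive performance.

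At stake is how the ROC curve and AUC of the filtered models are read. Beside the Tier A and all-analyte models, which use no significance filter, the filtered panel will tend to look better even if no marker predicts anything. This happens just when Tier A has found no candidate and a new panel is most welcome. Primary and secondary conclusions are not touched.

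**Working it through.** The SAP states no AUC, so there is no figure to reproduce. The order of steps was tested by simulation under the null, where the true AUC is 0.50.

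**Inputs from the SAP**

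- Subjects (1.4): "with approximately 96 subjects randomized per treatment group", with 25% drop-out by Week 12. One arm: 96 × 0.75 = 72. Both arms: 192 × 0.75 = 144. The drop-out figure fits the SAP's own sample size: 48 per group for a difference of 4, SD 8, one-sided alpha 0.125 and 90% power, so 2 × 48 / 0.75 / 0.90 = 142.2, against 142 stated.
- Candidates (5.1 less hsCRP and Tier A): ACTH, adiponectin, BDNF, IGF1, leptin, saliva cortisol and serum cortisol, which is 7. With the SNPs, 7 + 92 = 99. If hsCRP and the ten Tier A analytes may re-enter, the non-SNP count is 7 + 1 + 10 = 18.
- Filter: p ≤ 0.1 on HDRS17 change, adjusted for BMI, sex and age (covariates carried over from 5.2.1 and 5.2.2.1).

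**Assumptions**

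- Gaussian analytes; additive SNPs with allele frequency 0.1 to 0.5; independent markers unless stated.
- HDRS17 change with SD 8 (from 1.4); baseline mean 23, SD 3.5.
- Responders are the best 35% or 40% by percent change.
- A ridge model for response, fitted on 80% and tested on 20%.
- About 4,000 runs per scenario; Monte Carlo standard error of the mean AUC at most 0.004.

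**Expected number passing the filter under the null.** 99 × 0.1 = 9.9 (simulated 9.8 to 10.0) and 7 × 0.1 = 0.7 (simulated 0.7). The chance that none of 7 passes is 0.9^7 = 0.48 (simulated 47-48%).

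**Mean test AUC with the filter run on all subjects**

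| Candidates | n | Mean AUC |
|---|---|---|
| 99, independent | 72 | 0.70 |
| 99, independent | 96 | 0.68 |
| 99, independent | 144 | 0.65-0.66 |
| 99, SNPs in blocks of 4 or 8 (latent r = 0.9) | 72 | 0.65 or 0.63 |
| 18 | 72 | 0.61-0.62 |
| 18 | 144 | 0.59 |
| 7 | 72 | 0.61 |
| 7 | 144 | 0.57 |

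The 18-candidate rows come from additional runs (2,000 per scenario). The 7-candidate figures average over runs in which at least one analyte passed.

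**The same with the filter inside the training 80%.** With 99 candidates and n = 72 the mean is 0.50. An AUC of 0.70 or more occurs in 13% of runs, against 52-53% when the filter uses all subjects. The unfiltered all-analyte model also centres on 0.50.

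**Second simulation.** Event rates of 30% and 15%, n of 72, 96, 144 and 192, 7 or 99 candidates, 1,500 runs each. With the filter on all subjects, the mean is 0.68-0.70 (99 candidates, n = 72-96), 0.64-0.66 (99, n = 144-192), 0.60-0.61 (7, n = 72-96) and 0.57-0.58 (7, n = 144-192). With the filter in the training data only, it is 0.49-0.50. The bias was upward in all 16 scenarios.

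**Accuracy.** It moves little against always predicting non-response: 0.65 against 0.60 with 40% responders, and 0.67 against 0.65 with 35%.

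**Test-set size.** One arm: 0.2 × 72 = 14.4, about 14, or 0.2 × 96 = 19.2, about 19, without drop-out. Both arms: 0.2 × 144 = 28.8, about 29, or 0.2 × 192 = 38.4, about 38. For 14 test subjects with 5 responders, the null SD of the AUC is √[(14 + 1) / (12 × 5 × 9)] = 0.167. The simulated SD of an unbiased single-split AUC at n = 72 is 0.17, with a 95% range of 0.18 to 0.83.

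**The case against.** - **The order is inferred.** The SAP never says in so many words that the filter uses all samples. True, and the sponsor may have intended otherwise. But the filter refers to the tabulated models and the split is attached only to the machine-learning step, so a programmer following the text would filter on everyone. No other section corrects this.
- **The 0.70 is the top of a range.** It needs the SNPs as candidates, independent of one another, and one arm only. The SAP does not settle whether SNPs are among the analytes, and 5.2.2.2 names no arm; only 5.2.1 restricts to sirukumab. This stands, so the size has to be given as a range. Every reading tried still lies above 0.50.
- **The filtered panel need not look better.** Under the null, its AUC exceeds that of the all-analyte model in 58-68% of runs with 7 analytes (given that one passes) and in 78-87% with 99. So it tends to look better but does not always, and accuracy barely moves. This stands.
- **The small test set and the missing AUC interval apply to Tier A as well.** Correct. They are separate from the leak and are optional improvements.
- **It is exploratory and conditional, and an unfiltered comparator is reported.** This limits the severity. It does not make the hold-out valid. An unfiltered AUC near 0.50 beside an inflated filtered one could be read as evidence that the filter found signal. The false discovery rate adjustment corrects the univariate table, not the AUC.

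**Conclusion.** The concern holds. Followed as written, section 5.2.2.2 gives an upward-biased test AUC for the models filtered at p ≤ 0.1. Under the null the mean is about 0.57 to 0.70 instead of 0.50: the lower end with 7 candidates and both arms, the upper end with 99 independent candidates and one arm. These sizes rest on the assumed ridge learner, event rates and marker structure, and they are illustrative. The upward direction does not depend on a particular choice among the scenarios examined. The fault is confined to this one exploratory model set and feeds no decision rule in the SAP. It should be fixed, because the split is there to give an honest estimate and this one would not.

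**What to change.** Add to 5.2.2.2 a sentence such as: *For the multivariate models, the p ≤ 0.1 univariate filter and any scaling or tuning are carried out within the training data only and applied unchanged to the test data; if no analyte passes, no filtered model is reported.* The full-sample univariate table with false discovery rate values stays as a descriptive output.

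Cross-validation with the filter repeated inside each fold is an acceptable alternative to the single split. Optionally, give each test AUC a confidence interval, in Tier A as well, since the test sets are small.

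The cost is one or two sentences and a little computing. The reported AUC of the filtered models will be less favourable. Sometimes there will be no filtered model: in about 48% of null cases if only 7 analytes are candidates.

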6. PHARMACOKINETICS AND IMMUNOGENICITY

6.1. Pharmacokinetic Analyses

Serum sirukumab concentrations will be summarized over time. Descriptive statistics, including arithmetic mean, standard deviation (SD), median, interquartile range, minimum, and maximum will be calculated at each sampling time point. Monoaminergic antidepressants concentration data before and after sirukumab treatment, will also be summarized.

Data will be listed for all subjects with available serum concentrations.

All concentrations below the lowest quantifiable concentration or missing data will be labeled as such in the concentration database. All subjects and samples excluded from the analysis will be clearly documented in the study report.

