(1) To explore the efficacy of adjunctive sirukumab compared to adjunctive placebo, based on the change from baseline to 12-week endpoint in the Inventory of Depressive Symptomatology – Clinician Rated 30 Item Scale (IDS-C30). (2) To explore immunesystem related biomarkers (hsCRP, cytokines, chemokines), as well as other mood disorder related biomarkers (growth factors, hypothalamic–pituitary–adrenal (HPA) axis markers, metabolic markers) and to explore the potential correlation between these biomarkers and the clinical response, non-response or safety parameters of sirukumab. (3) To explore genetic and epigenetic variation that may be related to clinical response, non-response, or safety parameters of sirukumab (4) To explore the effect of sirukumab on the pharmacokinetics of monoaminergic antidepressants. (5) To explore the relationship between the severity of childhood trauma as assessed through the Childhood Trauma Questionnaire and the change in HDRS₁₇ scores following adjunctive sirukumab or placebo.

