1.3. Statistical Hypothesis for Trial Objective(s)

The primary hypothesis of this study is that sirukumab will determine significant improvement in depressive symptoms from baseline compared to placebo when administered as an adjunctive treatment to a monoaminergic antidepressant in the treatment of patients with MDD who have shown a suboptimal response to standard oral antidepressant therapy and have a screening hsCRP $\geq 0.300 \text{ mg/dL}$ (SI 3.00 mg/L), demonstrated by improvement in depressive symptoms from baseline to 12-week endpoint in the Hamilton Depression Rating Scale (HDRS17) total score.

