2.5.4. Pharmacokinetic and Immunogenicity Analyses Sets

Pharmacokinetic analyses will be performed on pharmacokinetic analysis set. It will include all randomized subjects who receive at least 1 administration of sirukumab in the double-blind phase and have at least 1 sample obtained after sirukumab treatment.

Immunogenicity analyses will be performed on immunogenicity analysis set. It will include all randomized subjects who receive at least 1 administration of sirukumab and have appropriate samples for detection of antibodies to sirukumab (ie, subjects with at least 1 sample obtained after sirukumab treatment).

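### The only analysis for the effect of sirukumab on antidepressant concentrations is a before/after summary without the placebo arm, which cannot separate a drug effect from drift

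*SAP*

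**What the plan says.** The fourth exploratory objective in section 1.1 reads: "To explore the effect of sirukumab on the pharmacokinetics of monoaminergic antidepressants".

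Section 6.1 answers it in one sentence: "Monoaminergic antidepressants concentration data before and after sirukumab treatment, will also be summarized". It names no treatment groups, no split by antidepressant, no handling of dose and no contrast.

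The population is fixed in section 2.5.4: "Pharmacokinetic analyses will be performed on pharmacokinetic analysis set". That set consists of "all randomized subjects who receive at least 1 administration of sirukumab in the double-blind phase", with the further condition of at least one sample taken after sirukumab. Neither a predose sample nor an antidepressant sample is required.

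The design has a concurrent control. Section 1.4 states: "Approximately 192 subjects will be enrolled in this study, with approximately 96 subjects randomized per treatment group". The primary objective in section 1.1 describes the comparator as placebo added to antidepressant therapy, so both arms take background drugs. No other section of the SAP summarises antidepressant concentrations.

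**The concern.** The objective is a causal question: what does sirukumab do to antidepressant exposure? Concentrations of a background drug can move over 12 weeks for other reasons, such as a change in adherence, in antidepressant dose or in sampling time. A before/after summary in one arm takes in all of these. The placebo arm is the natural gauge of them, and the set definition removes it. The definition suits sirukumab concentrations, which placebo subjects do not have. It does not suit antidepressant concentrations, which placebo subjects can have.

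Pairing is a second weakness. One post-dose sample is enough for entry, so the before and after summaries can describe different subjects once people leave or miss samples.

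What is at stake is objective 4 alone. A drift could be read as an interaction, or a real interaction could be hidden by a drift in the opposite direction.

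**Working it through.** The SAP gives no figure on this point, so there is none to reproduce. The argument rests on reading sections 1.1, 2.5.4 and 6.1 together. The drift sizes, standard deviations and per-drug numbers below are assumptions, not SAP values.

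**1. What each summary estimates.** Work with geometric mean after/before ratios. Let T be the true effect of sirukumab, and D and D' the drift ratios in the sirukumab and placebo arms.

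- Before/after in the sirukumab arm: T × D.
- Before/after in the placebo arm: D'.
- Ratio of the two: T × D / D', which equals T when D = D'.

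**2. No true effect (T = 1).** With shared drift of 5%, 10% or 20% downwards (D = 0.95, 0.90, 0.80), the one-arm summary is expected to show 0.95, 0.90 or 0.80. The between-arm ratio is expected to show 1 in each case. This needs no assumption about variability.

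**3. Masking.** With an effect T = 1.10 and a drift D = 0.90, the one-arm summary is expected to show 1.10 × 0.90 = 0.99, so the effect disappears.

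**4. Subject mix.** Suppose nobody's concentration changes, but a fraction 0.25 contributes a before value and no Week 12 value. That is the drop-out rate in section 1.4, applied here to the whole arm: 96 × 0.75 = 72 remain. It is an upper figure, because subjects who leave before any post-dose sample are not in the set. If leavers start 10% to 20% below stayers, the ratio of arithmetic means is

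- 10% lower: 1 / (0.75 + 0.25 × 0.90) = 1 / 0.975 = 1.026;
- 20% lower: 1 / (0.75 + 0.25 × 0.80) = 1 / 0.95 = 1.053.

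An apparent rise of about 3% to 5% arises from drop-out alone. Requiring pairs removes it.

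**5. What the control costs in precision.** With n subjects per arm and SD s of the within-subject log change, the one-arm variance is s²/n and the between-arm variance is 2s²/n, so the standard error is √2 ≈ 1.41 times as large. For an assumed 10 subjects per drug per arm and s = 0.3 to 0.5, the between-arm standard error is 0.134 to 0.224. Using the 75% level of section 4.1.1 only as a yardstick (multiplier 1.150), the half-width is 0.154 to 0.257 on the log scale, a factor of about 1.17 to 1.29. Per-drug contrasts would be unbiased under shared drift, but rough.

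**The case against.** The strongest reply is that section 6.1 promises a description and nothing more. It sets no test, interval, threshold or rule for a conclusion, and the objective is one of five exploratory ones. That stands, and it limits the severity. It does not remove the mismatch: no other analysis serves an objective worded as an effect of sirukumab.

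A second reply is that sampling belongs to the protocol, which is not shown. Whether placebo subjects give antidepressant samples, or have them assayed, is indeed unknown, so the fix must be conditional. But the analysis set and the summary are the SAP's own content, and the placebo arm is excluded there by definition. Section 6.1 also says "Data will be listed for all subjects with available serum concentrations". This may bring placebo values into view, but a listing is not a comparison.

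A third reply is that drift need not be shared. If efficacy differs between arms, adherence or dose changes may differ too, and then D / D' is not 1. This is correct, and is why dose changes should be taken into account.

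Three stronger readings are tempting, and the SAP supports none of them.

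- A reader might infer that the plan will attribute drift to sirukumab. It nowhere says so.
- A reader might calculate how often a confidence interval for the before/after ratio would wrongly exclude 1. No such interval is planned, and the answer depends on pooling. For an assumed 10% drift and SD 0.3 to 0.5, it is 74% to 97% with 72 subjects pooled over all drugs, but about 35% to 50% with 10 per drug. Neither is an error rate of this trial.
- A reader might infer that the primary result is affected. The primary analysis in section 4.2.2 is a randomised between-group contrast and takes no input from this summary. An interaction would be a mechanism behind an HDRS17 difference, not a bias in it.

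**Conclusion.** The point holds as a minor one. As written, section 6.1 with section 2.5.4 cannot answer exploratory objective 4, because with no sirukumab effect the expected before/after change equals the drift, and the set does not ensure that the same subjects stand on both sides. The size of any drift cannot be judged from the SAP. The conclusion that the summary is uncontrolled rests only on the SAP's wording. The benefit of adding placebo rests on two assumptions: that antidepressant samples exist in that arm, and that most of the drift is common to both arms. Section 5.2.1 already applies the same principle when it repeats the hsCRP models in placebo subjects to show specificity. Efficacy conclusions are untouched.

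**What to change.** - **Section 2.5.4:** keep the present set for sirukumab concentrations. Add an antidepressant concentration set: dosed subjects of both arms with a predose and at least one post-dose antidepressant concentration.
- **Section 6.1:** summarise the within-subject change by antidepressant and randomised group. Show the sirukumab-versus-placebo contrast descriptively where numbers allow, and take antidepressant dose changes into account, for example by dose-normalising or by flagging subjects whose dose changed.
- **If placebo samples are not available:** state in section 6.1 that the before/after change is descriptive and cannot be attributed to sirukumab.

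Separate ratios for metabolites are not asked for, since the SAP does not say that metabolites are assayed.

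The cost is SAP wording and one extra table. Per-drug cells will be small, and the between-arm contrast is less precise than the one-arm change, by the factor of about 1.41 in standard error shown above. If placebo samples are held but not yet assayed, the assays are a further cost.
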